3. OBJECTIVE(S) AND ENDPOINT(S)

	Objectives		Endpoints
Pri	mary		
•	To compare the effect of UMEC/VI 62.5/25 mcg with TIO/OLO 5/5mcg once daily on lung function in subjects with moderate COPD over 8 weeks of treatment.	•	Clinic visit trough FEV ₁ at Week 8
Ot	hers		
•	To compare the effect of UMEC/VI 62.5/25 mcg with TIO/OLO 5 /5mcg on other measures of efficacy and measures of health- related quality of life	•	Proportion of responders according to FEV₁ (a responder is defined as a ≥100mL change in Trough FEV₁ from baseline) at Week 8 Rescue albuterol/salbutamol use (percentage

Objectives	Endpoints			
	 of rescue-free days and mean number of Inhalations/day) captured in e diary Trough FEV₁ at Week 4 Trough FVC at Weeks 4 and 8 Trough IC at Weeks 4 and 8 COPD Assessment Test (CAT) score at Weeks 4 and 8 Proportion of responders according to CAT (defined as a ≥1 unit improvement in score from baseline) at Weeks 4 and 8 Time to clinically important deterioration composite endpoint Inhaler ease of use Inhaler errors Assessment of respiratory daily symptoms over Weeks 1-8 using Evaluating Respiratory Symptoms - COPD (E-RS) and its subscales (breathlessness, cough and sputum and chest symptoms) 			
Exploratory				
To compare the effect of UMEC/VI 62.5/25 mcg with TIO/OLO 5 /5mcg on other measures of efficacy and measures of health- related quality of life	 Rescue albuterol/salbutamol use (percentage of rescue-free days and mean number of Inhalations/day) over Weeks 1-8 using eMDI as data allow 			
To evaluate safety and tolerability of UMEC/VI 62.5/25 mcg and TIO/OLO 5/5mcg	 Incidence of adverse events (AEs) Incidence of COPD exacerbations 			

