2. SUMMARY OF KEY PROTOCOL INFORMATION

2.1. Changes to the Protocol Defined Statistical Analysis Plan

Any changes from the originally planned statistical analysis specified in the protocol GlaxoSmithKline Document Number 2015N256437_00 are outlined in Table 1.

Protocol		Re	porting & Analysis Plan		
Statistic	al Analysis Plan	Sta	tistical Analysis Plan	Ra	tionale for Changes
• Time deteri	to clinically important ioration composite endpoint	•	Time to clinically important deterioration composite endpoint will not be analysed	•	Study deemed too short to assess and SGRQ is not collected.
 Propo accor ≥1 ur from 	ortion of responders ding to CAT (defined as a hit improvement in score baseline) at Weeks 4 and 8	•	Proportion of responders according to CAT (defined as a ≥ 2 unit improvement in score from baseline) at Weeks 4 and 8	•	Typographical error
 ITT p All rai exclu rando who i run-ir rando be rai other rando consi rando Displa treatr was r 	opulation definition ndomized subjects, ding those who were omized in error. A subject s recorded as a screen or a failure and also omized will be considered to ndomized in error. Any subject who receives a omization number will be dered to have been omized. ays will be based on the nent to which the subject andomized.	•	ITT population definition now includes – received at least one dose of study medication. All randomized subjects, excluding those who were randomized in error and received at least one dose of study medication. A subject who is recorded as a screen or run-in failure and also randomized will be considered to be randomized in error. Any other subject who receives a randomizet on have been randomized. Displays will be based on the treatment to which the subject was randomized.	•	For consistency with prior GSK573719 + GW642444 studies
• No In	haler Naive population	•	Inhaler Naive population definition All subjects in the ITT population who have not used either Ellipta or Respimat for 6 months prior to inhaler evaluation (Visit 2	•	Population for Inhaler summaries and analysis

Table 1 Changes to Protocol Defined Analysis Plan

Protocol	Reporting & Analysis Plan	
Statistical Analysis Plan	Statistical Analysis Plan	Rationale for Changes
	 or Visit 5). This population will be used for all Inhaler assessment displays unless stated otherwise. 	

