2.2. Study Objective(s) and Endpoint(s)

Objectives	Endpoints			
Primary Objectives	Primary Endpoint			
To compare the effect of UMEC/VI 62.5/25 mcg with TIO/OLO 5/5mcg once daily on lung function in subjects with moderate COPD over 8 weeks of treatment.	 Trough FEV₁ at Week 8 			
Other Efficacy Objectives	Other Efficacy Endpoints			
To compare the effect of UMEC/VI 62.5/25 mcg with TIO/OLO 5 /5mcg on other measures of efficacy and measures of health-related quality of life	 Proportion of responders according to FEV1 (a responder is defined as a ≥100mL change in Trough FEV₁ from baseline) at Week 8 Rescue albuterol/salbutamol use (percentage of rescue-free days and mean number of Inhalations/day) captured in e diary Trough FEV₁ at Week 4 Trough FVC at Weeks 4 and 8 COPD Assessment Test (CAT) score at Weeks 4 and 8 COPD Assessment Test (CAT) score at Weeks 4 and 8 Proportion of responders according to CAT (defined as a ≥2 unit improvement in score from baseline) at Weeks 4 and 8 Inhaler ease of use Inhaler errors Assessment of respiratory daily symptoms over Weeks 1-8 using Evaluating Respiratory Symptoms - COPD (E-RS) and its subscales (breathlessness, cough and sputum and chest symptoms) 			
Exploratory Objectives	Exploratory Endpoints			
 To compare the effect of UMEC/VI 62.5/25 mcg with TIO/OLO 5 /5mcg on other measures of efficacy and measures of health-related quality of life 	 Rescue albuterol/salbutamol use (percentage of rescue- free days and mean number of Inhalations/day) over Weeks 1-8 might using eMDI 			
Safety	Safety Endpoints			
 To evaluate safety and tolerability of UMEC/VI 62.5/25 mcg and TIO/OLO 5/5mcg 	 Incidence of adverse events (AEs) Incidence of COPD exacerbations 			

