8.1.2.3. Rescue Medication

Mean number of Puffs/Occurrences of Rescue Medication Endpoints

- Mean number of puffs per day of rescue medication over the study duration (Weeks1-8) captured using e-diary
- Percentage of rescue-free days over the study duration (Weeks 1-8) captured using e-diary

Ме	an number of Puffs/Occurrences of Rescue Medication
٠	Mean number of occurences per day of rescue medication over the study duration (Weeks1-8)
	captured using e-MDI
•	Percentage of rescue-free days over the study duration (Weeks 1-8) captured using e-MDI
Мо	del Specification for MMRM Analysis Weeks 1-8
٠	Each endpoint derived for Weeks 1-2, 3-4, 5-6 and 7-8 will be analysed using a MMRM
	analysis using all available values recorded during Weeks 1-2, 3-4, 5-6 and 7-8.
•	The following covariates will be included in the model: period baseline, mean baseline, period,
	treatment, two-weekly period, two-weekly period by period baseline interaction and two-weekly
	period by mean baseline interaction.
•	The overall treatment effect will be estimated.
•	Two models will be fitted for each endpoint; one with a response variable of mean number of
	puffs/day or percentage of rescue-free days, and one with a response variable of the change
	from baseline.
•	An unstructured covariance structure for the R matrix will be used by specifying 'type=UN' on
	the REPEATED line.
•	The Kenward and Roger method for approximating the denominator degrees of freedom and
	correcting for bias in the estimated variance-covariance of the fixed effects will be used.
Ex	ample SAS code
	proc mixed data=start:
	class subject period treatment 2wkperd:
	model endpoint=period treatment 2wkperd mean base period base
	2wkperd*period base 2wkperd*mean base /
	ddfm=kr:
	random intercept / subject=subject:
	repeated 2wkperd / subject=subject*period type=un:
	Ismeans treatment / cl diff e :
	ods output Ismeans=Ismeans:
	ods output diffs=diffs:
	run:
Мо	del Checking & Diagnostics
•	Refer to Appendix 11: Model Checking and Diagnostics for Statistical Analyses
Mo	del Results Presentation
	The LS mean and LS mean change from baseline over Weeks 1-8 with their corresponding
•	Ses will be presented for each treatment together with the estimated treatment difference
	(IMEC/VI 62 5/25 vs. $TIO/OI O 5/5$) corresponding 95% CI and p-value
•	Percentage of rescue-free days will have LS mean with over Weeks 1-8 with their
•	corresponding SEs will be presented for each treatment, together with the estimated treatment

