10.5.2. Baseline Definition & Derivations

10.5.2.1. Baseline Definitions

For all endpoints (except as noted in baseline definitions) the baseline value will be the latest pre-dose assessment.

Baseline definitions are applicable to each period.

Parameter	Study Assessments Considered As Baseline	Baseline Used in Data Display
	Day 1 (Pre-Dose)	
FEV ₁ and FVC		
Trough FEV₁ and FVC	X	Mean value (30 min and 5 min pre-dose) recorded before dosing on Day 1 of each period. If one of the values is missing then the baseline will be the single remaining value
IC		× ×
Trough IC	X	Mean value (30 min and 5 min pre-dose) recorded before dosing on Day 1 of each period. If one of the values is missing then the baseline will be the single remaining value
Rescue Use		
Mean Number of Puffs of Rescue	Х	The total puffs of rescue for each day will be calculated as number of salbutamol puffs. If

Parameter	Study Assessments	Baseline Used in Data Display
	Considered As Baseline	
Medication Per Day and Percentage of Rescue-free Days Over Weeks 1-8 captured using e- diary	Day 1 (Pre-Dose)	the number of puffs is missing then the total puffs will be set to missing for that day. Provided at least half the days within the summary period have non-missing values the baseline is calculated over the duration stated below: Period 1: Values recorded between the latest of (7 days prior to Visit 2 and the day of Visit 1) and the Day before Visit 2 Period 2: Values recorded between the latest of (7 days prior to Visit 5 and the day of Visit 4) and the Day before Visit 5.
Mean Number of Occurrences of Rescue Medication Per Day and Percentage of Rescue-free Days Over Weeks 1-8 captured using e- MDI	X	The total occurrences, defined as >1 puff within a 2 minute time window, of rescue for each day will be calculated. Baseline is calculated over the duration stated below: Period 1: Values recorded between the latest of (7 days prior to Visit 2 and the day of Visit 1) and the Day before Visit 2 Period 2: Values recorded between the latest of (7 days prior to Visit 5 and the day of Visit 4) and the Day before Visit 5. Where entries of occurrences are not present the number of occurrences is assumed to be 0.
CAT		
CAT	X	Value recorded before dosing on Day 1 of each period
E-RS	·	

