- Occurrence is defined as >1 puff within a 2 minute time window.
- For each summary period, the mean number of occurrences per day and the percentage of rescue free days, will be calculated, using last dose-first dose+1 as denominator.
- Rescue use will be summarised over the periods defined above.

EXACT PRO

EXACT Respiratory Symptoms

- The EXACT-PRO (Evidera, 2016) is a 14-item daily diary (typically completed at bedtime). The daily E-RS total score (and subscales) will be computed according to the E-RS in COPD user manual [Evidera, 2016].
- The weekly mean scores for E-RS, and the subscales RS-Breathlessness, RS-Cough and Sputum, and RS-Chest Symptoms will be calculated as the mean of the daily scores in the weekly intervals defined above.
- Mean weekly score = (sum of daily scores/# diary days completed). If fewer than 4 days of data are available in any 7-day period, a mean weekly score should not be calculated. If fewer than 3 days worth of data are available in the 6-day period (day 50 to day 55) then a mean weekly score should not be calculated.

Calculation of Daily eDiary endpoints

E-RS Responder

- E-RS Total Score Responder: on-treatment weekly mean change from baseline E-RS total score ≤ -2
- E-RS Total Score Non-responder: on-treatment weekly mean change from baseline E-RS total score > -2
- E-RS Breathlessness Responder: on-treatment weekly mean change from baseline E-RS Breathlessness subscale score ≤ -1
- E-RS Breathlessness Non-responder: on-treatment weekly mean change from baseline E-RS Breathlessness subscale score > -1
- E-RS Cough Responder: on-treatment weekly mean change from baseline E-RS Cough & Sputum subscale score ≤ -0.7
- E-RS Cough Non-responder: on-treatment weekly mean change from baseline E-RS Cough & Sputum subscale score > -0.7
- E-RS Cough & Sputum Responder: on-treatment weekly mean change from baseline E-RS Chest Symptoms subscale score ≤ -0.7
- E-RS Cough & Sputum Non-responder: on-treatment weekly mean change from baseline E-RS Chest Sypmtoms subscale score > -0.7

CAT		
CAT Score		
• The CAT consists of eight items each formatted as a six-point differential scale: 0 (no impact) to 5 (high impact). A CAT score will be calculated by summing the non-missing scores on the eight items. The score can have values ranging from 0 to 40.		
• If one item is missing, then the score for that item is set as the average of the non-missing items. If more than one item is missing, then the CAT score will be set to missing.		

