			Weeks 1-8 using e-diary					
2.24.	ITT	E_T09	Summary of Mean Number of Puffs of Rescue Medication per Day using eMDI		SAC			
2.25.	ITT	E_T11	Summary of Percentage Rescue-free Days using eMDI		SAC			
CAT								
2.26.	ITT	E_T02	Summary of CAT Score	Include baseline	SAC			
2.27.	ITT	E_T03	Analysis of CAT Score		SAC			
2.28.	ITT	E_T08	Summary and Analysis of Proportion of Responders According to CAT		SAC			
E-RS								
2.29.	ITT	E_T02	Summary of Weekly Mean E-RS Total Score		SAC			
2.30.	ITT	E_T02	Summary of Weekly Mean E-RS - Breathlessness Score		SAC			
2.31.	ITT	E_T02	Summary of Weekly Mean E-RS - Cough and Sputum Score		SAC			
2.32.	ITT	E_T02	Summary of Weekly Mean E-RS - Chest Score		SAC			
2.33.	ITT	E_T03	Analysis of Weekly Mean E-RS Total Score		SAC			
2.34.	ITT	E_T03	Analysis of Weekly Mean E-RS - Breathlessness Score		SAC			
2.35.	ITT	E_T03	Analysis of Weekly Mean E-RS - Cough and Sputum Score		SAC			
2.36.	ITT	E_T03	Analysis of Weekly Mean E-RS - Chest Score		SAC			
2.37.	ITT	E_T08	Summary and Analysis of Proportion of Responders According to E-RS Total Score		SAC			

Efficacy: Tables								
No.	Population	IDSL / TST ID / Example Shell	Title	Programming Notes	Deliver-able			
2.38.	ITT	E_T08	Summary and Analysis of Proportion of Responders According to E-RS Breathlessness Score					
2.39.	ITT	E_T08	Summary and Analysis of Proportion of Responders According to E-RS Cough and Sputum Score		SAC			
2.40.	ITT	E_T08	Summary and Analysis of Proportion of Responders According to E-RS Chest Score		SAC			
Inhaler Ease of use								
2.41.	IN	(example 200301)	Summary of Ease of Use Questionnaire		SAC			
2.42.	IN	(example 200301)	Summary and Analysis of Ease of Use Rating	Present by sequence and total	SAC			
2.43.	IN	(example 200301)	Summary of Ease of Use Rating	Present by sequence and total (example 200301)				
Inhaler Er	rors							
2.44.	IN	(example 200301)	Summary of Errors for the ELLIPTA Inhaler	Raw questionnaire data	SAC			
2.45.	IN	(example 200301)	Summary of Errors for the Respimat Inhaler	Raw questionnaire data	SAC			
2.46.	IN	(example 200301)	Summary of Number of Subjects with at least One Error	Include critical and overall. Present by sequence and total	SAC			

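### The SAP is inconsistent on whether the exploratory eMDI rescue summary counts puffs or multi-puff occurrences; under the occurrence rule an isolated single puff counts as nothing

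*SAP*

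**What the plan says.** **Places that use inhalations or puffs per day**

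- Protocol section 3, exploratory endpoint: "mean number of Inhalations/day) over Weeks 1-8 using eMDI as data allow".
- SAP 2.2, the same endpoint: "mean number of Inhalations/day) over Weeks 1-8 might using eMDI".
- SAP 8.1.2.3, summary presentation: it describes a summary of mean puffs per day, then says that only these summaries, without the analysis, are repeated for eMDI data.
- SAP 10.13.5, Table 2.24: "Summary of Mean Number of Puffs of Rescue Medication per Day using eMDI". It uses display shell E_T09, the same shell as eDiary Table 2.20.

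**Places that use occurrences per day**

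- SAP 8.1.1, Table 5, the e-MDI row.
- SAP 8.1.2.3, endpoint list: "Mean number of occurences per day of rescue medication over the study duration (Weeks1-8", captured by e-MDI.
- SAP 10.5.2.1: "The total occurrences, defined as >1 puff within a 2 minute time window, of rescue for each day will be calculated".
- SAP 10.6.4: "Occurrence is defined as >1 puff within a 2 minute time window".

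**Change list.** SAP 2.1 says that "Any changes from the originally planned statistical analysis specified in the protocol" are set out in Table 1. Table 1 has four entries: time to clinically important deterioration dropped, the CAT responder threshold, the ITT definition, and the Inhaler Naive population. The eMDI measure is not among them.

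**Days without data.** For eMDI, SAP 10.6.4 scores a day as rescue-free when the puff total is missing. For the eMDI baseline, SAP 10.5.2.1 says "Where entries of occurrences are not present the number of occurrences is assumed to be 0". Protocol 6.2 makes supply of the devices depend on availability. SAP 10.7.2 sets a general rule: missing numerical data are not imputed outside the primary-endpoint sensitivity analysis, and subjects with missing data are generally left out of percentage denominators.

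**Denominator.** For each eMDI summary period, SAP 10.6.4 divides by last dose minus first dose plus one, without saying which dose.

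**The concern.** A programmer cannot satisfy all of these passages. If 10.6.4 is followed, the output is not the endpoint in Protocol section 3, and the title of Table 2.24 misdescribes its content. If the table title and the repeated puffs summary are followed, the occurrence definition is unused. The choice would be made at programming, with nothing in the change list to alert a reader.

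The occurrence rule also drops information. Rescue taken as single puffs, more than two minutes apart, contributes nothing to occurrences per day. Yet the companion measure, rescue-free days, is judged on puffs, so those same days are not rescue-free. An objective device record is most useful beside the diary, and occurrences per day cannot be compared with eDiary puffs per day.

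A second, smaller issue is that the eMDI rules do not separate a day with no rescue use from a day with no device.

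**Working it through.** The documents give no figure for the eMDI endpoint, so there is nothing to reproduce. The check applies the stated rules to simple use patterns and then compares the passages on missing data and the denominator.

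**1. The occurrence rule**

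Take a 14-day window, a working device every day, and 14 as the denominator. 'Apart' means more than two minutes between puffs.

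- Puffs per day = total puffs / 14.
- Occurrences per day, SAP rule = number of groups of more than one puff within two minutes / 14.
- Occurrences per day, alternative = number of groups of one or more puffs, grouping puffs within two minutes, / 14.
- Rescue-free days = days with no puff recorded / 14.

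| Daily use | Puffs/day | Occurrences/day, SAP rule | Occurrences/day, one or more puffs | Rescue-free days |
|---|---|---|---|---|
| One isolated puff | 14/14 = 1.0 | 0/14 = 0 | 14/14 = 1.0 | 0/14 = 0% |
| Two single puffs, apart | 28/14 = 2.0 | 0/14 = 0 | 28/14 = 2.0 | 0/14 = 0% |
| Two puffs together | 28/14 = 2.0 | 14/14 = 1.0 | 14/14 = 1.0 | 0/14 = 0% |

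In the first two rows the SAP rule reports no rescue occurrences while the companion table reports no rescue-free days. Rows two and three have the same number of inhalations but 0 against 1.0 occurrences per day. These results follow from the definitions alone; how common each pattern is cannot be taken from the documents.

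**2. Days without a device**

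On a working device, a blank day is the natural record of no use, so scoring it zero is reasonable there. Where no device was issued, the specific rules in 10.6.4 and 10.5.2.1, read literally, also give a rescue-free day and a baseline of 0. The general rule in 10.7.2 points the other way. The SAP does not say which governs. The eDiary has explicit safeguards: a denominator of non-missing days, at least one entry per time period (both in 10.6.4), and at least half the baseline days present (10.5.2.1). The eMDI rules have no counterpart.

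**3. The denominator**

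- If the dose is study drug: the Period 1 baseline window in 10.6.4 ends the day before Visit 2, and the first study dose is at Visit 2. A span between study doses contains no day of that window, although 8.1.2.3 asks for baseline and change-from-baseline summaries.
- If the dose is rescue: a subject with no rescue use in a window has no first or last dose, so the denominator is undefined for exactly the subjects who are fully rescue-free.

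Neither reading serves every window the SAP requires.

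**The case against.** **The SAP has not cleanly replaced the endpoint.** A reader might infer that inhalations per day has been abandoned. The documents do not support that: SAP 2.2, the repeated puffs summary in 8.1.2.3 and Table 2.24 with its shared shell all keep it. The mock shells are in a separate document. This objection stands, so the point is inconsistency, with a wrong quantity if 10.6.4 is followed.

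**The threshold may be a slip for one or more puffs.** Possibly, but the same wording appears in both 10.5.2.1 and 10.6.4, and it would be programmed as written.

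**The change may not belong in Table 1.** Protocol 9.4.1 specifies no eMDI analysis, and 9.4.2 leaves full details to the RAP. That softens the omission. It does not remove it, because Table 1 does list endpoint-level changes such as the CAT responder threshold.

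**A general missing-data rule exists.** SAP 10.7.2 would tend to keep subjects without a device out of percentage denominators, and the protocol treats eMDI data as conditional throughout. A reader might infer that rescue-free days will be overstated. Nothing says that subjects without a device enter these tables, and the share of such subjects is unknown. What stands is that the specific and general rules are not reconciled.

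**The denominator is tied to each summary period.** That wording in 10.6.4 argues against applying a whole-treatment span to a two-week window, so no numerical error should be claimed there. The undefined dose and the Period 1 baseline problem remain.

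**Conclusion.** The point holds as a minor one. SAP Table 5, the 8.1.2.3 endpoint list, 10.5.2.1 and 10.6.4 specify a different quantity from Protocol section 3, SAP 2.2, the repeated summary in 8.1.2.3 and Table 2.24, and Table 1 is silent. If the occurrence definition is programmed as written, isolated single puffs are not counted, and the two eMDI summaries can contradict each other for the same subject. The handling of days without a device and the meaning of dose in the denominator are incompletely specified.

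The size across the trial cannot be stated, since the documents give neither the frequency of single-puff use nor device coverage. A reader might infer a bias between treatments; no direction is shown, and none should be claimed. The consequence is limited to exploratory tables that SAP 8.1.2.3 summarises without analysis. Protocol 7.4.2 makes the eDiary the primary rescue measure, and the non-inferiority conclusion on trough FEV₁ is unaffected.

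**What to change.** 1. Summarise mean eMDI-recorded puffs per day. This matches the stated endpoint and Table 2.24. Align Table 5, the 8.1.2.3 endpoint list, 10.5.2.1 and 10.6.4 with it.
2. If occurrences are also kept, define one as one or more puffs, with puffs within two minutes grouped. List the addition in SAP Table 1 and give it its own correctly titled table.
3. Restrict the eMDI tables to subjects issued a device. Use as denominator the calendar days of each summary window already defined in 10.6.4, and of the baseline window, on which the subject had an issued device. Score zero use only on those days, and say that this takes precedence over 10.7.2 for eMDI data.

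The cost is a few lines of SAP text. Subjects without a device leave these tables. The rule assumes that device issue is recorded per subject. The eCRF is not among the documents, and the rescue inhaler dispensing and collection rows in Protocol 7.1 are as needed or as required (footnotes 8 and 9), so they cannot date device fitting by themselves. A device that was issued but not fitted or not recording would still score as zero use unless the device data show it; the SAP should state that limit.

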8.1.2.6. Inhaler assessment summaries

Inh	Inhaler Error Assessment							
En	dpoint							
•	Percentage of subjects making at least one critical error							
•	Percentage of subjects making at least overall error							
•	See Section 10.6.4 for error derivation.							
Su	Summary of Results Presentation							
٠	Summarized by inhaler, response (at least one error critical and overall) using n and %.							
	Results will be presented by sequence and total.							
•	The number and percent of subjects reporting each error for each individual question will also be presented (separate table for each inhaler).							

Sta	itistical Analysis of Inhaler Ease of Use Assessment
En	dpoints
•	Ease of use' rating for the ELLIPTA DPI compared with the Respimat.
Мо	del Specification
•	Each question will be analysed using the Cochran-Mantel-Haenszel test adjusted for country The Cochran-Mantel-Haenszel test serves as a stratified approximation to Prescott's test a
•	variation of a one-sample chi-square test that accounts for study inhaler sequence and difference in ease of use response [Prescott, 1981; Senn, 2002]. Homogeneity among country with respect difference in to ease of use will be assessed using a Breslow-Day test. Results of this test will not be reported on the final data display. See Section 10.6.4 for ease of use derivation.
Exa	ample SAS code
•	SAS code for stratified approximation to Prescott's test for each preference question:
•	ods output CMH = cmhi (where = (upcase(AltHypothesis) =: 'ROW MEAN SCORES') keep = AltHypothesis Prob) ; proc freq data = pref_data ; tables country * seq * ease_ord / cmh ;
	run ;
•	SAS code for checking brestow-Day rest for 2x2
	proc freq data = pref_data (where = (ease_ord ne 0)) ; tables country * seg * ease_ord / cmb :
Мо	del Results Presentation
•	P-values will be presented for the comparison between inhalers on the summary table
Su	mmary Results Presentation
•	Responses to the Ease of Use questionnaire will be summarised by inhaler, question/item
	and type of responses for the IN population.
•	The percentage preference (rated higher for Ellipta, rated higher for Respimat, rated the same) will be summarized on the same table as the analysis results detailed above. Results will be
	presented by question, sequence and total.
•	An additional summary will be produced based on the difference between the ratings for
	the two inhalers. The rating are coded as Very Easy=1, Easy=2, Neutral=3, Difficult=4,

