• If the language of the CAT conducted at a post-baseline visit is different to the language used at baseline, the CAT score for that visit and all subsequent visits will be set to missing		

CAT Responder

- A subject will be a responder if their on-treatment CAT score has decreased at least 2 units from baseline CAT total score.
- A subject will be considered a non-responder if their on-treatment CAT score has decreased by less than 2 units, has not changed, or has increased compared to baseline.
- Missing data will be handled as detailed in Section 10.7.2.

Inhaler Assessment			
Ease of Use			
• Ease of Use questionnaire consists of 5 ordinal responses: very easy (1), easy (2), neutral difficult (4) and very difficult (5), for each question. 'Very easy' is considered as the highest rating while 'very difficult' is considered as the lowest rating. Subjects answer each question regarding to ELLIPTA inhaler and 'Other' inhaler, respectively.	(3), n		
An ordinal variable (ease_ord) will be derived to based on the ease of use rating for each inhaler and based on the sequence of inhaler use. This variable will be used in the statistic analysis for ease of use data.	al		
 If the sequence of inhaler use is ELLIPTA inhaler in 1st period and RESPMIMAT inhaler in period, then for each ease of use question ease_ord = -1, if subject's ease of use rating for ELLIPTA inhaler is higher ease_ord = 1, if subject's ease of use rating for RESPMIMAT inhaler is higher ease_ord = 0, if subject's ease of use rating are the same with both inhalers 	2nd		
 If the sequence of inhaler use is RESPMIMAT inhaler in 1st period and ELLIPTA inhaler in period, then for each preference question ease_ord = 1, if subject's ease of use rating for ELLIPTA inhaler is higher ease_ord = -1, if subject's ease of use rating for RESPMIMAT inhaler is higher ease_ord = 0, if subject's ease of use rating are the same with both inhalers 	2nd		

Critical Error Variable

- Whether a subject had at least one critical error and at least one overall error (critical and noncritical) will be derived for each inhaler.
- Table below shows critical errors in bold.
- Responses in () indicate an error.

Respimat		
Preparation for first use	(0 = No) 1 = Yes	
Keep cap close. Press safety catch and	(0 = No) 1 = Yes	
pull off clear base		
Cap still closed. Insert narrow end of	(0 = No) 1 = Yes	
cartridge into inhaler and gently push		
against a firm surface to ensure that it		
has gone all the way in		

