Cap still closed. Replace clear base	(0 = No) 1 = Yes	
Cap still closed. Turn clear base in	(0 = No) 1 = Yes	
direction of the arrows on the label		
until you hear a click		
Flip cap open until it clicks into open	(0 = No) 1 = Yes	
position		

Critical Error Variable	
Point inhaler towards ground and	$(0 = N_0) 1 = V_{00}$
nress dose release button. Close can	(0 - 10) 1 - 165
and repeat stops 4.6 until the mist is	
visible. Then repeat stors 4.6 another	
2 times hefere use	
S times before use	0 = No (1 = Yes)
No cool by the line round the	$0 = N_0 (1 = V_{00})$
No seal by the lips round the	0 - NO(1 - res)
Deity lies	
Daily Use	0 = NO I = Yes
	("Not applicable to derived
	errors as question not
	appropriate to study design)
Keep cap closed. Turn clear base in	(0 = No) 1 = Yes
direction of the arrows on the label	
until you hear a click	
Flip cap open until it clicks into open	(0 = No) 1 = Yes
position	
Breathe out slowly and fully then close	(0 = No) 1 = Yes
your lips around mouthpiece	
While taking in a slow deep breath	(0 = No) 1 = Yes
press dose release button ; keep	· · · · · · · · · · · · · · · · · · ·
breathing in slowly	
Close cap	(0 = No) 1 = Yes
Ellip	ta
Failed to open cover	0 = No (1 = Yes)
Shook the device upside down after	0 = No (1 = Yes)
dose preparation	
No exhalation before an inhalation	0 = No (1 = Yes)
Exhaled directly into mouthpiece	0 = No (1 = Yes)
No seal by the lips round the	$0 = N_0 (1 = Yes)$
mouthpiece during the inhalation	
Inhalation manoeuvre:	$0 = N_0 (1 = Y_{es})$
- long	
- steady	
- deep	
Blocked air inlet during inhalation	$0 = N_0 (1 = Y_{es})$
manoeuvre	
Did not hold breath	$0 = N_0 (1 = Y_{es})$
Did not close the device	$0 = N_0 (1 = Y_{es})$
(Note: this is an error but one which	0 - 10 (1 - 163)
does not affect the medication that is	
inholod)	
mmuleuj	I

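### In the SAP's inhaler-error checklist, the Ellipta inhalation item describes the manoeuvre without a negation, yet its code makes Yes the error

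*SAP*

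**What the plan says.** Protocol 7.4.4.2 has the investigator or a designee complete an errors checklist at Visits 2 and 5. It evaluates the proportion of subjects with at least one critical error and with at least one error of any kind. The checklist is based on the patient leaflets, and instructions for completing it are left to the SPM.

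SAP 10.6.4 (Critical Error Variable) turns the checklist into data. For each inhaler it derives "Whether a subject had at least one critical error and at least one overall error", and its scoring rule is "Responses in () indicate an error". Critical items are to be recognised by bold type.

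The Ellipta list has nine items, all coded 0 = No (1 = Yes). Eight describe something done wrong, for example "Failed to open cover", "No exhalation before an inhalation" and "Did not hold breath". The ninth is headed "Inhalation manoeuvre" and lists three attributes: long, steady, deep.

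The results are reported as numbers and percentages under SAP 8.1.2.6, whose first endpoint is "Percentage of subjects making at least one critical error". The displays are Table 2.44 (Ellipta, item by item), Table 2.45 (Respimat, item by item) and Table 2.46 (at least one error, critical and overall), all in the Inhaler Naive population.

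**The concern.** Long, steady and deep describe a correct inhalation through the Ellipta. With no negative word in the row, Yes most directly means that the inhalation had those qualities. The scoring rule then makes that Yes an error, and makes No, a poor inhalation, free of error.

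The derived variables are at-least-one indicators, so a single reversed item is enough to put a subject in the error category. A programmer who follows the SAP to the letter could produce an Ellipta overall-error percentage made up largely of subjects who inhaled well. The nearest Respimat item is scored in the expected direction, so the two columns of the descriptive comparison would rest on opposite treatments of much the same skill.

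**Working it through.** The SAP states no figure to reproduce here. The check is a comparison of wording with code, followed by the scoring rule applied by hand.

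**1. Wording against code (SAP 10.6.4)**

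| Item | Worded as | Error response | Consistent? |
|---|---|---|---|
| Ellipta: "Failed to open cover" | fault | Yes | yes |
| Ellipta: "No exhalation before an inhalation" | fault | Yes | yes |
| Ellipta: "Did not hold breath" | fault | Yes | yes |
| Ellipta: five others (shaking, exhaling into the device, lip seal, blocked inlet, not closing) | fault | Yes | yes |
| Ellipta: "Inhalation manoeuvre" (long, steady, deep) | attributes, no negation | Yes | **no** |
| Respimat: "While taking in a slow deep breath" (with dose release) | correct step | No | yes |
| Respimat: lip seal | fault | Yes | yes |

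The code follows the wording from item to item, and it changes direction within the Respimat list when the wording changes. The Ellipta inhalation row is the exception.

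**2. A faultless Ellipta user**

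- As printed: eight fault items answered No give 0 errors, and the inhalation item answered Yes gives 1. The total is 0 + 1 = 1 error in 9, so an overall error is recorded.
- With wording and code aligned: 0 errors in 9, so no overall error.

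**3. Share flagged by this item alone**

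Let e be the true share of subjects whose inhalation is faulty. The documents give no value, so e is an assumption. As printed, the item flags 1 − e; once corrected, it flags e.

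| e (assumed) | Flagged as printed | Flagged when corrected |
|---|---|---|
| 0% | 100% | 0% |
| 5% | 95% | 5% |
| 10% | 90% | 10% |
| 20% | 80% | 20% |

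The overall-error percentage as printed cannot be lower than 1 − e.

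**4. Net effect on the overall-error percentage**

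Take the subjects with no error on the other eight items. Let g be the share of all subjects who are in this group and inhale correctly, and b the share who are in it and inhale poorly.

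- As printed: overall error = 1 − b.
- Corrected: overall error = 1 − g.
- Difference: (1 − b) − (1 − g) = g − b.

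The percentage is therefore inflated whenever correct inhalation is more common than poor inhalation among subjects who are otherwise free of error. Subjects with another error count either way, so the inflation is smaller the more of them there are. Protocol 7.4.4.2 scores the first use from the leaflet, without instruction that day, so neither e nor the other error rates can be presumed negligible.

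**The case against.** The strongest reply is that the row is a shorthand label. It is a heading with three attributes and no verb, inside a list of faults. A reader might take it to mean a fault in the manoeuvre (not long, not steady or not deep), in which case Yes as the error is right. The checklist item itself is in the eCRF and SPM, which are not among the documents, and its stem may be negative. The text of this table is also visibly damaged in places, and one Respimat row appears to have lost its label, so a lost word cannot be excluded.

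Much of this stands. It means that the code may be right and the printed wording the only fault. It does not remove the discrepancy: this row's own words read cleanly, nothing elsewhere in the SAP supplies a negation, and the SAP is the text from which the variable will be programmed.

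Three further limits also stand:

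- Bold type is not preserved in the text available, so it is unknown whether the item is critical. Only the overall-error variable is certainly exposed.
- No test of inhaler errors is specified. SAP 2.4 names them among the endpoints on which inference may be drawn, but Table 5 and SAP 8.1.2.6 plan summaries only.
- The item-level counts in Table 2.44 would probably reveal a reversed item, because it would be flagged in most subjects. That is a chance of catching the mistake after programming, not a specification that prevents it.

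A reader might go further and infer that the item reverses the comparison of Ellipta with Respimat. The documents do not support that. They give no expected error rate for either inhaler, so there is no direction to reverse. The shares in the working rest on assumed values of e.

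**Conclusion.** As printed, wording and code disagree on one of nine Ellipta items, and the literal rule counts correct technique as an error. If it were programmed that way, every faultless Ellipta user would be recorded with an overall error. The Ellipta overall-error percentage would be inflated by g − b, provided that correct inhalation is the commoner state among subjects with no other error. The descriptive comparison in Table 2.46 and the item count in Table 2.44 would be distorted to match. The critical-error percentage changes only if the item is critical.

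The conclusion rests on the SAP wording alone. It does not establish that the eCRF item is wrong or that data would be collected incorrectly. The endpoint is one of the protocol's other endpoints and is descriptive, and trough FEV1, non-inferiority and superiority are unaffected. This is a minor point, but worth settling because the resulting percentage could be badly wrong.

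**What to change.** Before programming Tables 2.44 and 2.46 and the derived error listing (Listing 42), compare the row with the eCRF checklist item.

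- If the eCRF stem is already negative, keep (1 = Yes) as the error and correct only the SAP wording, for example to say that the manoeuvre was *not* long, steady and deep.
- If the eCRF stem is positive, keep the wording and make No the error: (0 = No) 1 = Yes.

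At the same time, state whether long, steady and deep are one response or three, since only one code is printed, and confirm whether the item is critical.

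The cost is one cell in the SAP table and a look at the eCRF. No change to data collection, sample size or any model follows from it.
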